11.4.2.3 Time period and frequency for collecting adverse events

All AEs (including SAEs) will be collected from the insertion of the arterial catheter until the end-of-study visit.

Any AE with start date on the day IP administration must be recorded with start time.

At the end-of-study visit, information on new AEs or SAEs, if any, and stop dates for ongoing events must be recorded as applicable.

Investigators are not obligated to actively seek AEs or SAEs after conclusion of the study participation. However, if the Investigator learns of any SAE, including a death, at any time after a participant has been discharged from the study, and he/she considers the event to be reasonably related to the study intervention or study participation, the Investigator must promptly notify the Sponsor.

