9.2 Screening and enrolment log

Investigators must keep a record of all screened subjects even if they were not subsequently included in the study. This information is necessary to verify that subjects were selected without bias. The reason for screen failure should be stated for all subjects screened but not included. The reason for withdrawal should be stated for all subjects included but not completed.

A screening number will be allocated to each subject in connection to the informed consent process at the Screening visit. The screening number is generated automatically in the electronic case report Form (eCRF). The screening number will allow identification of subjects irrespective of their possible eligibility for the study.

Subjects included will be assigned a subject number (101, 102, 103 etc. for PART A and 201, 202, 203 etc. for PART B). The first digit will correspond to the study part, and the 2nd and the 3rd digits correspond to the subject number.

If a subject cannot receive the planned dose of IP within 28 days after screening (*i.e.*, the time interval between signing informed consent until dose administration) the subject should be rescreened before proceeding in the study.

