10 TREATMENTS

10.1 Identity of investigational products

The IPs will be supplied as the *myblu*™ e-cigarette system with e-liquid pods:

The *myblu*™ e-cigarette will be supplied together with a USB charger.

E-liquid pods will be supplied as:

- Pods for training purposes, containing 2.5% freebase nicotine formulation (no flavour) corresponding to Formulation 1.
- Pods for training purposes, containing 2.5% nicotine salt formulation (no flavour) corresponding to Formulation 2.
- Empty pods (for filling at the PET Centre with radiolabelled Formulation 1 and Formulation 2)

Bulk liquid Formulation 1 and Bulk liquid Formulation 2, will be supplied, for radiolabelling and filling of empty e-liquid pods at the PET Centre.

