11.2 Demographics and other baseline characteristics

11.2.1 *Informed consent*

Signed informed consent must be obtained before any screening procedures are initiated. The informed consent procedure is further described in Section 14.3.

11.2.2 *Eligibility criteria*

Eligibility criteria should be checked during screening and verified before IP administration. The criteria are specified in Sections 9.4 and 9.5.

11.2.3 *Demographic information*

The following demographic data will be recorded: gender, age, ethnicity and race.

11.2.4 ***Weight and height***

Weight and height will be measured without shoes. BMI will be calculated with one decimal from the height and weight recorded.

11.2.5 ***Medical/surgical history***

Medical/surgical history will be obtained by subject interview in order to verify that the eligibility criteria are met.

The medical/surgical history should include all relevant diseases and surgeries within 2 months prior to screening as judged by the Investigator.

11.2.6 ***Prior and concomitant medication***

Prior medications taken within 2 weeks will be obtained by subject interview in order to verify that the eligibility criteria are met (see also Section 9.6.2).

Medications are classified as prior if the stop date was before or on the day of the first dose administration (pre-dose) and as concomitant if ongoing on the day of the first dose administration, stopped after the first dose administration or started after the first dose administration. To distinguish between prior and concomitant medications on Day 1 in each part (i.e. the first IP administration), the start time of any newly introduced medication or the stop time of any previously ongoing medication must be recorded in the eCRF.

Any use of concomitant medication from screening until the last end-of-study visit must be documented appropriately in the subject's eCRF. Relevant information (i.e. name of medication, dose, unit, frequency, start and stop dates, reason for use) must be recorded. All changes in medication should be noted in the eCRF.

11.2.7 ***HIV and Hepatitis B/C***

Subjects will be tested for HIV, hepatitis B surface antigen and hepatitis C antibodies prior to inclusion into the study. Any positive result will exclude the subject from participating in the study.

11.2.8 ***Urine drug screen***

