Urine will be screened for drugs of abuse at timepoints outlined in the schedule of events (Table 8.1-1 and Table 8.1-2) using the Alere™ Drug Screen Test Panel.

11.2.9 ***Alcohol breath test***

An alcohol breath test will be performed at timepoints outlined in the schedule of events (Table 8.1-1 and Table 8.1-2).

11.2.10 ***Baseline symptoms***

A baseline symptom is defined as an event that occurs between the subject's signing of the ICF until the insertion of the arterial catheter (i.e. an event that occurs during the screening

period). Such events are not AEs and will be recorded as baseline symptoms in the Medical History Log in the eCRF.

11.2.11 *Clinical laboratory profile*

Blood samples for analysis of clinical chemistry and haematology will be collected through venepuncture or an indwelling venous catheter and sent to the certified clinical chemistry laboratory at Uppsala University Hospital and analysed by routine analytical methods.

The clinical laboratory parameters are defined in Table 11.2-1 and will be assessed at screening.

Abnormal values assessed by the Investigator as clinically significant will be reported as baseline symptoms. If an abnormal value is associated with corresponding clinical signs or symptoms, the sign/symptom should be reported in the Medical History Log in the eCRF.

Table 11.2-1 Clinical laboratory parameters

Category	Parameter
Clinical chemistry	Alanine aminotransferase (ALT)
	Aspartate aminotransferase (AST)
	Creatinine
	Glucose
Haematology	Haematocrit
	Haemoglobin (Hb)
	Platelet count
	Red blood cell (RBC) count
	White blood cell (WBC) count
FSH-test (at screening, postmenopausal females only in questionable cases)	FSH
	Estradiol

11.2.12 *Physical examination*

A complete physical examination will include assessments of the head, eyes, ears, nose, throat, skin, thyroid, neurological, lungs, cardiovascular, abdomen (liver and spleen), lymph nodes and extremities.

Physical examination will be judged as normal, abnormal, not clinically significant or abnormal, clinically significant. The assessment will be recorded in the eCRF.

11.2.13 *Resting 12-lead ECG*

Single 12-lead ECG will be recorded in supine position after 10 minutes of rest using an ECG machine. HR and PR, QRS, QT and QTcF intervals will be recorded.

ECGs will be reviewed and interpreted on-site by the Investigator.

Any abnormalities will be specified and documented as clinically significant or not clinically significant.

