11.3 Assessments related to PET-endpoints

11.3.1 *Inhalation training*

At the end of the screening visit subjects, who consented to study participation and are found eligible (awaiting results of clinical laboratory sampling), will perform inhalation training with the *myblu*™ e-cigarette. Training will be held by study personnel at the research site.

Inhalation training will be performed on dummy (nicotine free) devices and once on a regular *myblu*™ e-cigarette (containing nicotine corresponding to the formulations used during PET). Training on a nicotine-containing device is considered necessary for the subjects for them to be used to the experience when inhaling in the PET-camera.

Inhalation training on dummy devices (nicotine free) may be repeated in the morning of Visit 2 (before PET), if considered necessary by the study personnel or the subject.

11.3.2 *Insertion/removal of arterial catheter*

After a positive modified Allen test, an intraarterial catheter will be inserted preferably in the arteria radialis of the non-dominant arm if possible, else in another artery chosen by the anaesthesiologist. Local anaesthetics e.g. 0.5 mL of Xylocain® (active substance lidocaine) 10 mg/mL may be applied for the arterial cannulation at the discretion of the anaesthesiologist inserting the cannula.

Positive modified Allen test: If the hand flushes within 5-15 seconds, this indicates that the ulnar artery has good blood flow; this normal flushing of the hand is considered to be a positive test.

Negative modified Allen test: If the hand does not flush within 5-15 seconds, this indicates that ulnar circulation is inadequate or non-existent; in this situation, the radial artery supplying arterial blood to that hand should not be punctured.

The arterial catheter will be removed by trained personnel at the research clinic after the (last) PET session is completed. When the catheter is withdrawn, pressure should be applied to the injection site for approximately 10 minutes until bleeding ceases. The catheter is checked to see that it is intact.

11.3.3 *Assessment of blood radioactivity*

Discrete blood samples will be analysed using an in house developed well counter detector system cross-calibrated with the PET/CT scanner.

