11.4 Assessments related to secondary endpoints

11.4.1 *PET endpoints*

Refer to Section 11.3.

11.4.2 *Adverse events*

The Principal Investigator is responsible for ensuring that all medical staff involved in the study is familiar with the content of this section and the content of the CTC standard operating procedures (SOPs) regarding handling of AEs.

11.4.2.1 *Definition of adverse event*

An AE is defined as any untoward medical occurrence in a subject administered an IP and which does not necessarily have a causal relationship with this treatment. An AE can therefore be any unfavourable and unintended sign (including clinically significant abnormal values from relevant tests, such as clinical safety laboratory tests, ECGs, vital signs), symptom, or disease temporally associated with the use of an IP, whether or not considered related to the IP.

11.4.2.2 *Definition of serious adverse event*

An SAE is any AE which:

- results in death
- is life-threatening (this refers to a reaction in which the subject was at risk of death at the time of the reaction; it does not refer to a reaction that hypothetically might had led to death if the reaction was more severe)
- requires in-patient hospitalisation or prolongation of existing hospitalisation
- results in persistent or significant disability/incapacity
- is a congenital anomaly/birth defect
- is an important medical event (IME) (this refers to a reaction that may not be immediately life-threatening or result in death or hospitalisation, but may jeopardise the subject or may require intervention to prevent any of the other outcomes defined above)

Examples of IMEs are intensive treatment in an emergency room for allergic bronchospasm or blood dyscrasias, convulsions that do not result in hospitalisation, development of drug dependency, and drug abuse.

Planned hospitalisations or surgical interventions for a condition that existed before the subject signed the ICF and that did not change in intensity are not SAEs.

If there is any doubt as to whether an AE meets the definition of an SAE, a conservative viewpoint must be taken, and the AE must be reported as an SAE.

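### A reaction to the nicotine training inhalation at screening precedes AE collection, so the protocol does not require grading, causality assessment or, if it is serious, the 24-hour report

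*Protocol*

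**What the plan says.** **The exposure.** Protocol section 11.3.1 places training at the end of the screening visit, for subjects "who consented to study participation and are found eligible (awaiting results of clinical laboratory sampling), will perform inhalation training". It adds: "Inhalation training will be performed on dummy (nicotine free) devices and once on a regular" e-cigarette with nicotine matching the PET formulations. Any repeat on the morning of Visit 2 is limited to nicotine-free devices.

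**The product.** Section 10.1, which identifies the investigational products, includes "Pods for training purposes, containing 2.5% freebase nicotine formulation (no flavour) corresponding to Formulation 1" and a matching nicotine salt pod for Formulation 2.

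**The safety window.** Section 11.4.2.3 states: "All AEs (including SAEs) will be collected from the insertion of the arterial catheter until the end-of-study visit". Section 11.2.10 covers the time from consent to catheter insertion: "Such events are not AEs and will be recorded as baseline symptoms in the Medical History Log in the eCRF".

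**The definition.** Section 11.4.2.1 reads: "An AE is defined as any untoward medical occurrence in a subject administered an IP", whether or not the event is caused by it.

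**How the word IP is used elsewhere.** Section 9.2 sets a re-screening rule: "If a subject cannot receive the planned dose of IP within 28 days after screening", the subject must be screened again. Section 11.2.6 ties first administration to Day 1: "To distinguish between prior and concomitant medications on Day 1 in each part (i.e. the first IP administration"). Both schedules of events place IP administration at Visit 2 only.

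**The concern.** The study supplies a nicotine product, has subjects inhale it under supervision, and then classes whatever follows as background medical history until an arterial catheter goes in, up to 28 days later. The protocol itself names salivation, nausea and dyspepsia as known effects (6.3) and says freebase nicotine irritates the throat more than the salt (6.2). Entry requires daily cigarette smoking, not experience with e-cigarettes (9.4), so training may be a subject's first use of such a device.

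What is at stake is the handling of a serious or clearly related reaction at that visit. The rules that would make the investigator grade it, judge its cause and alert the sponsor within 24 hours are all written for AEs, and this event is declared not to be one. It is a reporting gap in a small trial, not a threat to the imaging results.

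**Working it through.** No figure in the protocol depends on this, so the check sets the sections side by side.

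1. **Order of events.** Consent, then nicotine training at the end of screening (Day -28 to Day -1), then catheter insertion on Day 1, when AE collection opens. The nicotine training inhalation therefore always falls in the baseline-symptom period.

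2. **What follows from not being an AE.** Intensity grading (11.4.2.4) and causality assessment (11.4.2.5) are required for AEs and recorded in the AE Log. Section 11.4.2.2 defines a serious adverse event (SAE) as a kind of AE, so an event outside the AE class cannot become an SAE. The 24-hour route in 11.4.2.10 starts from an entry in the AE Log. The clause in 11.4.2.2 on erring towards seriousness settles doubt about an AE; it does not turn a baseline symptom into one.

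3. **Does the status of the pods settle it?**
   - If the training pods are IP, as their place in 10.1 suggests, a reaction meets the definition in 11.4.2.1, and 11.2.10 and 11.4.2.3 contradict it.
   - If they are not IP, as 9.2, 11.2.6 and the schedules imply, the definition does not reach the reaction at all.

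   Neither reading leads to required grading or reporting.

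4. **Do other clauses close the gap?** The Product Form in 11.4.2.9 is for malfunctions and incidents with the e-cigarette system and carries no deadline. The last paragraph of 11.4.2.3 deals with SAEs learned of after discharge, so it presupposes an SAE.

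5. **Subjects who then fail screening.** Training takes place before laboratory results are back, so a trained subject can still be excluded. Section 11.2.10 still asks for a baseline-symptom record, but the stated minimum for screen failures in 9.7 is consent and the reason for failure.

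6. **Size.** There is one nicotine training use per trained subject.
   - Included subjects (9.3): 14 to 17.
   - Screened (9.3): about 25, so 25 - 17 = 8 to 25 - 14 = 11 are not included. How many of these would have been trained is not stated.
   - Training uses: from 14 to at most about 25. The upper end requires that nobody failed on anything known before training.
   - The protocol gives no reaction rate. If the rate of any reaction were 1% to 10% per use (an assumption), the whole trial would expect 14 x 0.01 = 0.14 to 25 x 0.10 = 2.5 reactions. This says nothing about serious ones, which would be fewer.

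**The case against.** The strongest reply is that the window was chosen on purpose. The safety objective (7.2, 7.3) concerns radiolabelled nicotine, and collection opens at the first invasive procedure on Day 1, before any labelled dose. That explains the choice, and it is why the planned safety summaries are unaffected. It does not resolve the conflict with 10.1 and 11.4.2.1, nor give a serious reaction to a study product a required route to the sponsor.

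Three stronger readings are tempting, and the documents do not support them.

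- **That such events are lost.** They go into the eCRF. Medical history is coded in MedDRA (16.6), presented by system organ class and preferred term, and listed by subject (17.4.2). A serious reaction might also lead to exclusion under criterion 2 of 9.5, and 9.2 requires a reason for every screen failure. These records carry no required grade, causality judgement or deadline.
- **That grading or reporting is barred.** No section forbids either. Section 11.4.2 also points to site standard operating procedures that are not shown, and 11.4.2.9 leaves the word incidents undefined. The protocol does not require these steps; it does not prohibit them.
- **That a third to a half of the nicotine risk goes unwatched.** The labelled sessions number 10 x 2 + 4 = 24 to 10 x 2 + 7 = 27. One can therefore compute that 14/(14 + 24) = 37% to 25/(25 + 24) = 51% of supervised nicotine occasions lie outside the AE window. That counts occasions, not risk or missed events, and its upper end needs every screened subject to be trained.

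**Conclusion.** The point holds as a gap in what the protocol requires and as an internal contradiction over what counts as IP. On either reading of the training pods, a reaction to the screening inhalation is recorded as medical history without a required grade, causality assessment or, if it is serious, 24-hour report.

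The expected number is small: one supervised use in each of about 14 to 25 daily smokers, at a rate the protocol does not give. The PET endpoints and the safety results from Day 1 onward do not change. The conclusion rests on the protocol text alone and assumes that the unseen site procedures do not add the missing requirement. It deserves correction because it concerns the safety of subjects exposed to a study-supplied product, and because the correction is cheap.

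**What to change.** 1. **Section 10.1:** state whether the training pods are IP, and reconcile this with the use of IP dose and IP administration in 9.2, 11.2.6 and the two schedules. If they are declared IP, the baseline definition (17.1) and the Safety Analysis Set (17.3.2), which both turn on IP administration, must be re-read as well. If they are declared study-supplied product outside that term, those sections can stand.

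2. **Section 11.4.2.3, one added sentence, with a matching exception in 11.2.10:** from the nicotine training inhalation onward, all SAEs and any event the Investigator considers related to that inhalation are entered in the AE Log, graded, assessed for causality and, if serious, reported within 24 hours. This includes subjects who then fail screening. All other events before catheter insertion remain baseline symptoms.

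3. **Sections 11.4.2.1 and 11.4.2.5:** extend the AE definition and the causality scale to the training inhalation. The second change is needed because the Probable, Possible and Unlikely categories are defined only against the IP, and no scale is given for study procedures.

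**Cost.** Text changes, and earlier use of a log and a reporting route that already exist; no new visit or procedure. A few more entries will be made, including some under screening numbers. Some will be hard to attribute, because subjects may go on smoking until midnight before the PET day (9.6.1).

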11.4.2.4 Assessment of intensity

The grading of the intensity of AEs will follow the common terminology criteria for adverse events (CTCAE) v5.0 [3]. Grade refers to the severity of the AE. The CTCAE displays Grades 1 through 5 with unique clinical descriptions of severity for each AE based on this general guideline.

The Investigator must assess the intensity of an AE using the following definitions, and record it on the AE Log in the eCRF:

- Grade 1** Mild; asymptomatic or mild symptoms; clinical or diagnostic observations only; intervention not indicated.
- Grade 2** Moderate; minimal, local or non-invasive intervention indicated; limiting age-appropriate instrumental activities of daily living (ADL)*.
- Grade 3** Severe or medically significant but not immediately life-threatening; hospitalisation or prolongation of hospitalisation indicated; disabling; limiting self-care ADL**.
- Grade 4** Life-threatening consequences; urgent intervention indicated.
- Grade 5** Death related to AE.

*Instrumental ADL refer to preparing meals, shopping for groceries or clothes, using the telephone, managing money, etc.

**Self-care ADL refer to bathing, dressing and undressing, feeding self, using the toilet, taking medications, and not bedridden.

11.4.2.5 Assessment of causal relationship

The Investigator must assess the causal relationship between an AE and the IP using the definitions below and record it the AE Log of the eCRF:

- Probable** The event has a strong temporal relationship to the IP or recurs on re-challenge, and another aetiology is unlikely or significantly less likely.

Possible The event has a suggestive temporal relationship to the IP, and an alternative aetiology is equally or less likely.

Unlikely The event has no temporal relationship to the IP or is due to underlying/concurrent illness or effect of another drug (that is, there is no causal relationship between the IP and the event).

An AE is considered causally related to the use of the IP when the causality assessment is probable or possible.

In addition, the Investigator will assess the causal relationship between an AE and the study procedures (e.g. injection site reaction, events in association with arterial catheter insertion, other arterial catheter associated AE).

11.4.2.6 Assessment of outcome

The Investigator must assess the outcome of an AE using the definitions below and record it on the AE Log of the eCRF:

Recovered/resolved The subject has recovered completely, and no symptoms remain.

Recovering/resolving The subject's condition is improving, but symptoms still remain.

Recovered/resolved with sequelae The subject has recovered, but some symptoms remain (for example, the subject had a stroke and is functioning normally but has some motor impairment).

Not recovered/not resolved The subject's condition has not improved and the symptoms are unchanged (for example, an atrial fibrillation has become chronic).

Fatal

Unknown

